6 STUDY DESIGN AND METHODS OF DATA COLLECTION AND DATA ANALYIS

Two sequential longitudinal implementation cohort studies with embedded qualitative interview studies. BOOST-IS assesses change in patient reported outcome measures after receiving the BOOST programme, as well as ascertaining the effectiveness and impact of the BOOST MOOC on knowledge and implementation of the BOOST programme.

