10-point managing symptoms item	X	х				
Satisfaction		х				
Single item physical activity question		x				
Activity over 16 days (wearable)	х	X				
Activity log	х	X				
Sleep efficiency	х	Х				

Therapist participants

All therapist data will be collected during stage 2 using JISC online surveys. Therapist demographics will be collected prior to starting the BOOST MOOC and will include name, email, sex, age, occupation, professional qualification, work setting, years of experience treating symptomatic LSS patients and average number of patients treated per month (if applicable). We will collect learning

outcomes and implementation intentions online at the end of the BOOST MOOC. Learning outcomes include self-reported course completion, perceived confidence (in their own ability) and capability (given wider external factors such as necessary space and equipment) to deliver the BOOST programme. Implementation outcomes align with the taxonomy proposed by Proctor et al (16) and include implementation intention (Adoption), satisfaction with the training (Acceptability) and potential barriers to implementation (Appropriateness) and actual use in practice (Adoption). Therapists will be emailed a link to a brief follow up questionnaire by the study team 6 months after completing the baseline assessment to assess additional implementation outcomes. We will again ask participants about self-reported course completion and actual use in practice (Adoption as well as asking them about the number of BOOST sessions delivered (Fidelity), perceived patient satisfaction with the BOOST programme (Acceptability), perceived clinical usefulness of the BOOST programme, helpful and unhelpful aspects of the BOOST programme with regards to implementation, and reasons for non-implementation (Appropriateness). Outcomes and timepoints are detailed in Table 3.

Table 3: Therapist participant outcomes and assessment time points

	Timepoint				
	Start of	On completion	6 months from		
Stage 2	MOOC	of MOOC	MOOC enrolment		
Informed consent	х				
Therapist demographics	х				
Course completion		х	x		
Satisfaction with training		х			
Confidence to deliver the BOOST programme		х	х		
Capability to deliver the BOOST programme		х	x		
Implementation intention		х	x		
Potential barriers to implementation		x	x		
Actual use in practice		х	x		
Perceived patient satisfaction			x		
Number of BOOST programme cycles delivered			х		
Perceived clinical usefulness of BOOST			x		

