Helpful / unhelpful aspects of BOOST			x		
Reasons for non-implementation			x		

Interview study

Therapist interviews in stages 1 and 2 will follow a semi-structured format. As per standard practice, these interviews will be guided by a pre-specified set of open-ended questions, allowing the use of interviewer prompts to further investigate participant responses, and allow the participant the scope to explore additional areas of the topic they feel relevant to their situation (17, 18). The interview guide will be informed by two frameworks: i) the integrated Promoting Action on Research Implementation in Health Services (i-PHARiS) and ii) the Theoretical Domains Framework (TDF) (15, 19). We will conduct interviews via MS Teams, use audio-visual recording and automated transcription. Interviews will be conducted at a convenient time for the participants, as close to the completion of the BOOST group sessions as possible.

Intervention fidelity

To ensure that the optimised BOOST programme is being delivered as intended, a BOOST study researcher will observe at least one individual and group treatment session at each site. An intervention checklist will be used to ensure that key session components have been delivered and feedback will be provided to the therapist where applicable. Additionally, we will collect the anonymised BOOST individual session logs, attendance and exercise logs, and phone call logs, to understand how the BOOST programme was delivered.

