Therapists who manage (or plan to manage) patients with symptomatic LSS in the UK will be invited to participate in a soft launch of the BOOST MOOC. This will not be publicly available, and therapists will need to agree to participate in the cohort study to gain access to it. We will target a minimum of 30 therapists and will recruit them through special interest groups and networks, conferences, University of Exeter, Keele and Oxford research group contact lists, Applied Research Collaboration regional websites, social media platforms, and personal contacts. Interested therapists will be asked to contact the BOOST study team to express their interest. Interested therapists will be sent a link to a webpage containing a participant information sheet, consent form and a baseline questionnaire prior to enrolment in the course. After providing informed consent and completing the baseline questionnaire, therapists

will be sent a link to enrol in the BOOST MOOC with instructions on how to create an account on FutureLearn. Once enrolled, therapists will have full access to the BOOST MOOC content. Therapists will be asked to complete the course within a six-week period from the date of registration.

Therapists who have completed the BOOST MOOC will be invited to participate in a cohort study to evaluate patient outcomes. We will target 10 NHS sites. Site can choose to deliver the BOOST programme within an NHS setting or to partner with a community provider for the delivery of the BOOST programme.

We will email the first 10 therapists to deliver the optimised BOOST programme in their practice to invite them to participate in a semi-structured interview.

Patient participant recruitment

Patient recruitment and study procedures are the same as those described in stage 1 above.

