8 STATISTICS AND ANALYSES

8.1 Sample Size

Stage 1

We will recruit a minimum of 24 participants and 3 therapists from NHS sites, and a minimum of 6 participants and 1 therapist from a community provider linked to an NHS Trust.

Stage 2

We will recruit a minimum of 60 patients and 10 therapists.

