Evidence from the counterfactual analyses will help inform assessment of whether the improvements in the intervention should be accepted. An attraction of the Bayesian framework is that it provides a

basis for making direct probability statements about whether a greater proportion of people achieve clinically significant outcomes in pain and walking with the improvements.

Data from the wrist worn accelerometer will be merged into the study dataset with all other participant outcome measures and will be included in the statistical modelling detailed above. We will also report descriptive summaries of all participant outcome measures.

Final decisions

Using data from a relatively smaller number of participants will not be definitive but will be reasonable to inform clinical practice. If our estimates from the propensity score analysis demonstrate that the point estimate of the optimised intervention is lying within the upper half of the distribution of the confidence interval of the original trial, we will take that as a positive marker. We will also consider the estimated posterior probability that the optimised intervention has improved outcomes from the Bayesian analysis and accept the new intervention if this is above 50%. If this probability estimate is below 50% or the point estimate from the propensity score analysis is lying below the original lower limit, then we will continue with the original intervention. If the two analyses diverge, the Bayesian approach will be taken as the primary analysis as it will be more sensitive. We will use qualitative interviews from the therapists delivering the optimised programme to determine whether the changes are manageable and appear effective. We will triangulate this data.

Stage 2: patient participant outcomes

We will collect outcome data from a minimum of 60 participants and follow the same data analysis plan as described for Stage 1. For implementation to be deemed successful and be launched widely via the FutureLearn BOOST MOOC, using comparison to the synthetic controls from the original trial, the benchmark will be that the estimates of changes in pain-related disability and walking are not significantly worse than the original trial.

Stage 2: therapist participant outcomes

Data will be analysed descriptively using IBM SPSS Statistics, version 28.0.1.0. Cases with missing values will excluded using listwise deletion. Free text responses will be coded using the TDF.

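### Listwise deletion does not fit a therapist survey with mutually exclusive items and can distort adoption in either direction; separately, the claimed MOOC impact on knowledge has no measure and no baseline

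*Protocol*

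**What the plan says.** Section 8.2 (Stage 2: therapist participant outcomes) fixes a purely descriptive analysis: "Data will be analysed descriptively using IBM SPSS Statistics, version 28.0.1.0". The next sentence sets the missing-data rule: "Cases with missing values will excluded using listwise deletion". It does not say whether deletion applies to one item, one survey or the therapist's whole linked record, or how an inapplicable item is treated.

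Section 6.1 and Table 3 list the items. The six-month survey includes "perceived patient satisfaction" and also "Reasons for non-implementation". Actual use in practice, the adoption item, is asked at the end of the MOOC and again at six months. At the start of the MOOC, Table 3 has only consent and demographics. "Confidence to deliver the BOOST programme" and the matching capability item first appear at completion. No knowledge item is listed at any timepoint.

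The design statement in section 6 describes the study as "ascertaining the effectiveness and impact of the BOOST MOOC on knowledge and implementation of the BOOST programme". Section 4.2 is narrower: its secondary objective concerns learning outcomes and intentions on completion of the course.

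The group is small. Section 7.2 says of the MOOC evaluation: "We will target a minimum of 30 therapists". Section 8.1 says for Stage 2: "We will recruit a minimum of 60 patients and 10 therapists".

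**The concern.** There are two separate problems.

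First, listwise deletion keeps only cases complete on a common set of items. A descriptive summary needs no common set, and this survey contains two items that no single therapist is expected to answer together. If either item is in the set and a blank counts as missing, a therapist who reported plainly whether BOOST was used can still be dropped. Those dropped differ from those kept in exactly the respect that the adoption figure is meant to describe. Even without routing, scattered blanks would shrink a group of about 30 for no benefit.

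Second, an effect of the MOOC on knowledge needs a measure of knowledge and something to compare it with. The plan has no such measure, no score before the course and no comparison group. The analysis cannot recover a baseline that was never collected, and the gap is permanent once a therapist has started the course.

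Assessing therapist learning and implementation is a stated Stage 2 aim (section 4.1), so both problems affect what the study can report on that aim.

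**Working it through.** The protocol gives no precision or sample-size derivation for the therapist outcomes, so there is no stated figure to reproduce. What follows is illustration.

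**Inputs.** N = 30 enrolled (section 7.2 minimum). A = 10 adopters is an assumption; it matches the section 8.1 minimum of therapists delivering BOOST but is not a predicted adoption rate. True adoption is then 10/30 = 33.3%. Response rates, item missingness and the coding of inapplicable items are not given, so they are varied.

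**Step 1: routed items.** Suppose that all 30 reply, and that a blank on an inapplicable item counts as missing.

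- Patient satisfaction in the listwise set: the 20 non-implementers are deleted, and adoption reads 10/10 = 100%.
- Reasons for non-implementation in the set: the 10 implementers are deleted, and adoption reads 0/20 = 0%.
- Both in the set: no case remains.
- Neither in the set, or inapplicable coded as a valid answer: adoption reads 10/30 = 33.3%.

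The stated rule does not say which of these applies.

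**Step 2: scattered blanks.** Table 3 has 7 items at MOOC completion and 11 at six months, 18 in all. With independent missingness of 5% per item (assumed), expected complete cases are N × (1 − 0.05)^k:

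- over the 11 six-month items: 30 × 0.95^11 ≈ 17;
- over all 18: 30 × 0.95^18 ≈ 12.

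With 2% missing per item the figures are about 24 and 21; with 10%, about 9 and 4.5.

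**Step 3: unequal retention.** Let rA and rN be the proportions of adopters and non-adopters kept in the analysis.

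- Reported adoption = A·rA / (A·rA + (N − A)·rN).
- Lower bound over all enrolled (unknowns counted as non-adopters) = A·rA / N.
- Upper bound (unknowns counted as adopters) = (A·rA + number not retained) / N.

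| rA / rN | Reported adoption | Lower bound | Upper bound |
|---|---|---|---|
| 80% / 80% | 8/24 = 33.3% | 8/30 = 26.7% | 14/30 = 46.7% |
| 90% / 60% | 9/21 = 42.9% | 9/30 = 30.0% | 18/30 = 60.0% |
| 90% / 40% | 9/17 = 52.9% | 9/30 = 30.0% | 22/30 = 73.3% |
| 60% / 90% | 6/24 = 25.0% | 6/30 = 20.0% | 12/30 = 40.0% |

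Equal retention gives no bias; the other rows go up or down. Where a therapist is lost through a blank on another item, item-by-item summaries recover the adoption answer. Where the whole six-month survey is missing, they do not; the bounds show what remains unknown.

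**Step 4: the learning claim.** No arithmetic applies. Change is the score after minus the score before. Table 3 has the after-score for confidence and capability, no before-score for either, and neither score for knowledge. The section 6 statement therefore has nothing to rest on. The section 4.2 objective does, because a description of scores on completion satisfies it.

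**The case against.** The strongest reply is that the rule may be harmless in practice. The analysis is descriptive, and if each item is tabulated alone, listwise deletion over that one item is the same as using the available cases. Coding of inapplicable items is ordinary analysis-plan detail. Reasons for non-implementation may be free text and go to thematic coding, outside any numerical set; its format is not stated. The number of cycles delivered can be answered as zero, and clinical usefulness can be an opinion formed in training, so patient satisfaction is the only item that clearly requires delivery. These points stand, and they limit what can be claimed. They do not rescue the rule: the protocol fixes a named method without a scope, and the benign reading amounts to not using that method.

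A reader might infer that listwise deletion overstates adoption. That needs adopters to be retained more often than non-adopters. It is plausible, but the documents give no response pattern, and the opposite pattern understates adoption. Nor are therapists who did not finish the course automatically lost: section 6.1 times the six-month survey from the baseline assessment and asks again about completion.

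A reader might also infer that no therapist can survive the deletion. That needs both routed items in one set and inapplicable answers counted as missing, and section 8.2 states neither.

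On learning, the fair reply is that section 4.2 promises only outcomes on completion, and that a before-after change without a comparator would still not isolate the MOOC's effect. Both are right. The conflict is with the wording of section 6.

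Finally, these are secondary objectives, and the benchmark in section 8.2 for wide launch rests on pain-related disability and walking, not on adoption.

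**Conclusion.** The point holds in two limited parts.

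Listwise deletion is the wrong rule for this survey. It can needlessly discard valid answers from about 30 therapists and distort adoption in either direction. With 10 adopters of 30 assumed, the retention patterns tried give 25% to 53% against a true 33%. Routing alone could give 100%, 0% or no cases under particular readings of the rule. All of these figures rest on assumed adoption, response and coding. They show sensitivity; they are not a forecast, and an upward bias is not established.

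The section 6 claim about knowledge cannot be met as designed, because no knowledge measure is listed and no learning score precedes the course. This needs no assumption beyond Table 3 and the accompanying text. The post-course objective in section 4.2 is unaffected.

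Both parts should be corrected, but neither touches the patient outcomes or the launch benchmark.

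**What to change.** **Section 8.2, therapist outcomes.** Replace listwise deletion with item-by-item summaries of available cases, each showing its denominator. Code routed items as not applicable, separately from missing. Report adoption and course completion with the number enrolled as a stated denominator, and give lower and upper bounds that count all non-responders one way and then the other. Which figure leads is a matter of judgement; counting non-responders as non-adopters is itself untestable, so the bounds should always accompany it. The number enrolled is obtainable because consent and the baseline questionnaire precede enrolment (section 7.2).

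**Section 6 and Table 3.** Add the existing confidence and capability items to the pre-enrolment questionnaire. Report paired change, using the ID that already links each therapist's surveys (section 9.6.2), and label it an uncontrolled before-after description. For knowledge, either add the same short item before and after the course, or delete the word from the section 6 design statement.

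**Cost.** A few sentences of protocol text and a few items on an online form already in use. The baseline form becomes slightly longer, and denominators will vary from item to item.

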9 ETHICAL AND REGULATORY CONSIDERATIONS

9.1 Declaration of Helsinki and Guidelines for Good Clinical Practice

The investigator will ensure that this study is conducted in accordance with the principles of the declaration of Helsinki, any relevant regulations and that the study is consistent with the guidelines for good clinical practice (last amended Fortaleza, Brazil, October 2013).

9.2 Assessment and management of risk

9.2.1 Serious Adverse Events

A serious adverse event is any untoward medical occurrence that:

- Results in death
- · Is immediately life-threatening
- Requires hospitalisation or prolongation of existing hospitalisation
- Results in persistent or significant disability or incapacity
- Is a congenital abnormality or birth defect

Other 'important medical events' may also be considered serious if they jeopardise the participant or require an intervention to prevent one of the above consequences.

NOTE: The term "life-threatening" in the definition of "serious" refers to an event in which there was a risk of death at the time of the event; it does not refer to an event which hypothetically might have caused death if it were more severe.

9.2.2 Adverse Events

Serious adverse events are likely to be very rare and highly unlikely to occur as a result of the exercise programme being delivered in this cohort study.

Given the age range of the study population and the nature of physical interventions, foreseeable occurrences (adverse events) that may occur during the study period which do not require specific time critical reporting, but may be collected as part of standard data collection are (refs):

- acute infections (e.g. viral)
- medical instability (e.g. diabetic control becomes hypoglycaemic, deterioration in control of heart failure)
- vestibular disorders and stroke
- fall-related injuries

However, if any of the above occur as the result of an incident during, or within two hours of completing, the exercise sessions or follow-on physical activities or are related to the intervention and categorised as an SAE according to 9.2.1, then they should be reported to the BOOST-IS Team as a suspected SAE as per section 9.2.3.

It is likely that participants taking part in an exercise programme may experience:

- transient increases in symptoms of neurogenic claudication (≤ 72 hours)
- delayed onset of muscle soreness (≤ 72 hours)

If either of these do not resolve in 72 hours, are assessed as being related to the study intervention, and are categorised as an SAE according to 9.2.1, then they should be reported to the BOOST-IS

Team as a suspected SAE as per section 9.2.3. Under these conditions, these events will be considered as unexpected, since they are more severe and longer lasting than what is expected.

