9.2.3 Reporting Procedures for Serious Adverse Events

Serious adverse events (SAEs) which occur as the result of an incident during, or within two hours of completing, the exercise sessions or follow-on physical activities, and are considered related to the study, will be reported in a pre-defined and time-critical process. The site PI or delegated team member must assess causality of any suspected SAEs and report them to the BOOST-IS Team within 24 hours of becoming aware of the event, using the Serious Adverse Event Form for non-CTIMPs. Completed forms will be scanned and emailed to the BOOST-IS Team, who will assess causality and expectedness, and ensure that all SAEs are followed up to resolution. Any unexpected SAE which is deemed related to the study interventions will be reported to the REC that gave a favourable opinion of the study by the BOOST-IS Team within 15 working days of the Chief Investigator becoming aware of the event, using the Health Research Authority (HRA) report of serious adverse event form (see HRA website).

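### Section 9.2.2 ties SAE reporting of a related, serious flare to lasting beyond 72 hours, a condition that 9.2.1 and 9.2.3 do not contain, and the reporting scope also differs between 9.2.2 and 9.2.3

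*Protocol*

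**What the plan says.** Section 9.2.1 defines a serious adverse event by its outcome. One criterion is "Requires hospitalisation or prolongation of existing hospitalisation". No criterion carries a minimum duration.

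Section 9.2.2 names two reactions that participants are likely to have: a temporary worsening of claudication symptoms and delayed muscle soreness, each described as lasting up to 72 hours. The escalation rule reads "If either of these do not resolve in 72 hours, are assessed as being related to the study intervention", and adds as a third condition that they count as an SAE under 9.2.1; such events then go to the BOOST-IS Team as suspected SAEs by the 9.2.3 procedure. The next sentence says that events meeting these conditions count as unexpected, because they are both more severe and longer lasting than expected.

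The same section lists four groups of "foreseeable occurrences (adverse events) that may occur during the study period which do not require specific time critical reporting": acute infections, medical instability, vestibular disorders and stroke, and fall-related injuries. These go to the team if they result from an incident during or within two hours of an exercise session or follow-on activity, *or* if they are related to the intervention and serious.

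Section 9.2.3 covers SAEs that result from an incident in that same window "and are considered related to the study, will be reported in a pre-defined and time-critical process". The site must assess causality and "report them to the BOOST-IS Team within 24 hours of becoming aware of the event". The team then assesses causality and expectedness. The last step is: "Any unexpected SAE which is deemed related to the study interventions will be reported to the REC", with a limit of 15 working days.

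**The concern.** Whether an SAE is reported, and how fast, should follow from its seriousness and its relation to the intervention. Section 9.2.2 adds a third condition, persistence, for the two reactions that the protocol itself regards as most likely. A site cannot know on day 1 whether a flare will last beyond 72 hours. A therapist who follows the specific rule in 9.2.2 would wait, while one who follows the general rule in 9.2.3 would report.

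The duration condition also reaches the ethics committee step, because the sentence that makes these events unexpected rests on the same three conditions. A serious flare that settles early is more severe than the described reaction but not longer lasting, and the text does not say how to class it.

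At stake is consistent and timely capture of serious, related reactions in people aged 65 and over who receive a modified programme. Section 5.2 adds an exercise in standing and allows delivery by community providers.

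**Working it through.** No sample size, error rate or event count is involved, and the plan gives no figure to reproduce. The check sets the conditions side by side and works through one timeline.

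**Conditions as written**

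| | Serious? | Related? | Duration? | Exercise window? |
|---|---|---|---|---|
| 9.2.1 (definition) | yes | – | none | – |
| 9.2.2, flare or soreness | yes | yes | unresolved at 72 h | none stated |
| 9.2.2, listed foreseeable events | yes, on the relatedness route | alternative to the window | none | alternative to relatedness |
| 9.2.3 (time-critical reporting) | yes | yes | none | yes, together with relatedness |

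**Timeline.** Take a related flare arising from a session that leads to admission on day 1.

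1. Under 9.2.1 it is serious on admission.
2. Let the site become aware of the serious event *a* hours after onset. The 9.2.3 deadline is then *a* + 24 hours after onset.
3. The 9.2.2 duration condition cannot be met before hour 72.
4. Overrun if the site waits for 9.2.2 = 72 − (*a* + 24) = 48 − *a* hours, and none once *a* reaches 48.
   - *a* = 0: 48 hours.
   - *a* = 24: 24 hours.
   - *a* = 48: 0 hours.
5. If the flare resolves before hour 72, the 9.2.2 condition is never met. Section 9.2.3 still makes the event reportable.

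**Scope.** Take a listed event that is serious and related but does not result from an incident in the session or two-hour window. Section 9.2.2 sends it to the team, because relatedness there is an alternative. Section 9.2.3, to which 9.2.2 refers it, requires the window *and* relatedness, so the event falls outside that section's stated scope. The two sections disagree about this event too.

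**The case against.** The strongest reply is that 9.2.3 stands on its own. It has no duration condition, and 9.2.2 says 'if', not 'only if'. A session-linked, related flare that leads to admission is therefore reportable whatever has happened by hour 72. This stands, and it rules out the stronger reading that such events are excluded or dropped. What remains is that 9.2.2 is the specific rule for these reactions and itself says when they enter the 9.2.3 procedure, so a site could reasonably follow it and wait. The 9.2.3 backstop also reaches only session-linked events.

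It is also fair that the two clocks start at different points. The 24 hours run from awareness and the 72 hours from onset, so 48 hours is a maximum.

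A reader might further infer that the foreseeable list lets a stroke or a fall-related injury caused by the programme be classed as expected and kept from the ethics committee. The documents do not support this as a rule. The protocol never equates foreseeable with expected. It sends related, serious listed events into the 9.2.3 procedure, and it calls SAEs "highly unlikely to occur as a result of the exercise programme being delivered in this cohort study", which points towards classing them as unexpected. Section 9.2.3 simply gives no reference for judging expectedness, and that warrants a clarification only.

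Nor is the ethics committee the only outside route for safety information. The section on the role of the sponsor requires arrangements to alert the sponsor and other organisations to significant safety developments. Section 9.3 provides for a final report to the committee, and for progress reports on request. These do not replace prompt SAE reporting, but they rule out a claim that no other route exists.

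**Conclusion.** The concern holds as a conflict between sections. For a related, serious, session-linked flare or soreness that is under 72 hours old or resolves within 72 hours, 9.2.3 requires a report within 24 hours of awareness, while 9.2.2 read alone does not yet, or never, requires one. The possible delay is up to 48 hours, assuming awareness at onset and a site that follows 9.2.2. The 'or' in 9.2.2 against the 'and' in 9.2.3 is a second mismatch, for listed events outside the exercise window.

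The practical size is small. The protocol calls SAEs very rare, and the event must be serious, related and short-lived or still recent. No analysis or estimate is affected. The change is worth making because it costs little and removes a conflict over events that the protocol itself names as likely reactions. The text does not support saying that duration overrides seriousness throughout the plan, or that listed events are withheld from the ethics committee.

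**What to change.** Reconcile 9.2.1 to 9.2.3 together:

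- In 9.2.2, remove the 72-hour condition from the SAE reporting and unexpectedness sentences. For example: a symptom flare or muscle soreness that is related to the intervention and meets any criterion in 9.2.1 is reported under 9.2.3 within 24 hours of awareness, whatever its duration, and is considered unexpected.
- Keep 72 hours only to describe the expected, non-serious reaction.
- Use the same scope in 9.2.2 and 9.2.3. State in both whether relatedness is sufficient on its own or is needed in addition to the session and two-hour window.
- As a minor clarification, state that appearing on the foreseeable list does not by itself make a related SAE expected for ethics committee reporting. There is no need to declare every related SAE unexpected, since that would make the expectedness assessment in 9.2.3 redundant.

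The cost is a few sentences in 9.2.2 and 9.2.3, handled as an amendment under 9.3.2, and possibly a few extra SAE forms. Treatment, data collection for outcomes and the analysis are unchanged.
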